1.5.2. Dose Rationale

The doses of voxelotor to be evaluated in this study are 1500 mg orally daily through 3000 mg administered by split dose twice daily (BID). This dose of voxelotor is supported by: 1) absence of concerning exposure-related safety findings with 1500 mg daily from the pivotal Phase 3 Study GBT440-031 in adults and adolescents with SCD; 2) demonstrating dose-dependent treatment effects of voxelotor on PD and efficacy measures; and 3) not yet achieving MTD with dose levels up to 2800 mg to date as a single dose in healthy volunteers and 1500 mg daily for multiple doses in healthy volunteers and participants with SCD. A conservative dose-escalation approach is undertaken with increments of 500 mg at a time, representing 33% increase at the lowest dose level and 20% increase at the highest, with careful monitoring and assessments prior to escalation to the next dose level. It is perceived, based on prior data, that voxelotor administration twice rather than once daily may result in favorable gastrointestinal tolerability.

See the IB for additional details.

2. STUDY OBJECTIVES

See Section 3 for details regarding the investigational plan.

2.1. Primary Objective

- To evaluate the tolerability and safety of voxelotor at daily doses of > 1500 mg (2000 mg to 3000 mg) in participants with SCD

2.2. Secondary Objectives

- To evaluate the change in Hb and hemolysis measures
- To evaluate the incidence of VOCs

2.3. Exploratory Objectives

- To evaluate the PD properties (effect on Hb-oxygen equilibrium curve [OEC]) as measured by P50 and P20
- To assess voxelotor pharmacokinetics (PK) as evaluated by population PK analysis and % Hb occupancy
- To evaluate the PK-PD relationship of voxelotor at daily doses of >1500 mg
- To evaluate the effects of voxelotor on Clinical Global Impression of Change (CGI-C) and Patient Global Impression of Change (PGI-C)

3. INVESTIGATIONAL PLAN

This study is an open-label, Phase 2 study of the tolerability and safety of voxelotor 2000, 2500, and 3000 mg in adult participants with SCD \geq 18 to $<$ 60 years of age.

3.1. Study Endpoints

Study endpoints are described in Section [10](#).

3.2. Study Design

This is an open-label, sequential period, within-participant dose escalation study. Up to 40 participants with SCD (HbSS or HbSB⁰) who are 18 to $<$ 60 years of age, inclusive, will be enrolled.

Study participants will undergo up to four periods of voxelotor administration at progressively higher dose levels from 1500 mg until either a MTD or 3000 mg daily dose is reached, whichever occurs first ([Figure 2](#)):

- Period 1: 1500 mg per day: 1500 mg once daily (3×500 mg tablets) for 3 weeks (± 3 days)
- Period 2: 2000 mg per day: 1000 mg (2×500 mg) BID for 3 weeks (± 3 days)
- Period 3: 2500 mg per day: 1500 mg (3×500 mg) in morning and 1000 mg (2×500 mg) in evening daily for 3 weeks (± 3 days)
- Period 4: 3000 mg per day: 1500 mg (3×500 mg) BID for 3 weeks (± 3 days)
- Observation Period: MTD or 3000 mg daily for 24 weeks
- Safety Follow-up Period: from day of last dose to 28 days postdose.

[figure not shown]
If at any time a dose level $>$ 1500 mg is not tolerated by a participant in the dose escalation period, the dose may be reduced to a previous level for the participant, which will then be administered for 24 additional consecutive weeks as an observation period. Dose modifications are allowed during the observation period in consultation with the Sponsor's Medical Monitor ([Appendix C](#)).

If 1500 mg daily is the MTD for a participant, then the participant may enter the observation period and continue to receive 1500 mg, for up to 24 weeks or until they are able to roll over into the open-label extension or receive commercial voxelotor, where available. If the participant discontinues early from the study, the participant will undergo an End of Study (EOS) visit approximately 28 days after the last dose and will not be eligible for the open-label extension study.

The safety of study participants will be closely monitored by the study team. In addition, a Safety Monitoring Committee (SMC) will review safety, tolerability, and available PK and PD data at regular intervals (Section [3.4](#)). Blood draws for PK and PD (including Hb and hemolysis markers), routine chemistry and hematology laboratory tests, and 12-lead ECGs in triplicate will be obtained periodically, as listed in the Schedule of Assessments ([Appendix A](#), [Appendix B](#)).

Individual stopping rules are specified in Section 3.7. Upon completion of the observation period for individual participants or after study termination, eligible participants will be given the option to enroll in an open-label extension study.

Figure 2: **Study Schema**

OLE, open-label extension.

3.3. Assessments

Assessments and procedures are described in Section 8, [Appendix A](#), and [Appendix B](#).

3.4. Safety Monitoring Committee

The SMC will closely monitor the safety of the study participants throughout the duration of study. The SMC will review the totality of safety, tolerability, and available PK and PD data to monitor safety.

The SMC will be composed of the Principal Investigator or designee and Sponsor representatives, including the Study Director/Medical Monitor, Clinician with disease expertise, Biostatistician, and Safety Scientist. Details of the scope, responsibilities, and frequency of the SMC will be provided in the SMC Charter.

3.5. Treatment

See Section 5 for voxelotor information.

3.6. Duration of Study Participation and of the Study

Study participation will be up to 44 weeks in duration, which includes up to 30 days in the Screening Period; 21 days (3 weeks) each in Periods 1, 2, 3, and 4; 168 days (24 weeks) in the Observation Period; and 28 days in the Safety Follow-up Period. See Section 3.2 for additional information regarding the study periods for this study.

The study will end when the last participant's last visit occurs.

3.7. Stopping Rules

3.7.1. Early Discontinuation of the Study/Study Stopping Rules

The Sponsor has the right to terminate this study at any time. Reasons for terminating the study may include, but are not limited to, the incidence or severity of TEAEs in this or other studies indicating a potential health risk to participants.

The study will be put on hold immediately with the first fatal case reported in participants (at any dose level greater than 1500 mg/day) considered to be related to study drug, until SMC reviews the data and determines whether it is reasonable to proceed.

In the instance of early termination of the study, the Sponsor will notify, in writing, the Investigators, regulatory authorities, and Independent Ethics Committees (IECs)/Institutional Review Boards (IRBs) and will specify the reason(s) for termination.

3.7.2. Cohort Dose Escalation Stopping Rules

- If ≥ 3 participants at a given dose level experience similar and related serious adverse events (SAEs), dose escalation will be paused until the SMC assesses the safety data and makes a recommendation.
- Progression to the next higher dose level can also be stopped if the SMC recommends discontinuation of dose escalation based on the totality of safety data.

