3.7.3. Early Discontinuation of Individual Participants

3.7.3.1. Individual Dose-limiting Toxicity Definition: Dose Escalation Period

Criteria for individual dose-limiting toxicity at doses beyond 1500 mg/day include, but are not limited to, the following:

- Any AE Grade ≥ 3 not clearly resulting from the underlying disease and deemed by the Investigator and/or Medical Monitor to be related to study drug.
- Worsening of an ongoing, treatment-related AE by ≥ 1 grade as per Investigator assessment
- Grade 3 nausea, vomiting, or diarrhea (deemed related to study drug) requiring hospitalization and/or intravenous fluids and parenteral tube feeding, total parenteral nutrition
- Study drug-related SAE

If any of these criteria is met, the Investigator should consider temporary dose reduction and/or study drug discontinuation for the individual participant after discussing with the Sponsor. If a subject discontinues early due to AEs, the subject will not be eligible for the open-label extension study.

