9.2. Adverse Event Reporting

9.2.1. General

All AEs will be recorded from the time the study participant signs the ICF until 28 days after the last dose of study drug. After this period, the Investigator should report only SAEs that are assessed as related to study drug until the EOS visit occurs. All SAEs must be reported within 24 hours of SAE awareness on the AE CRF via the electronic data capture (EDC) system. The Investigator is responsible for evaluating all AEs, obtaining supporting documents, and ensuring documentation of the event is complete. Details of each reported AE must include at minimum severity, relationship to study drug, duration and outcome. All (both serious and nonserious) AEs must be followed until they are resolved or stabilized, or until reasonable attempts to determine resolution of the event are exhausted.

Any participant who experiences an AE may be discontinued from study drug at any time at the discretion of the Investigator. The Sponsor and the CRO's Medical Monitors must be notified of the study participant's discontinuation.

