10.2. Determination of Sample Size

As this is an exploratory study to provide descriptive information on the tolerability, safety, and efficacy of voxelotor at dose levels > 1500 mg daily, the sample size chosen was based on previous experience in exploratory studies to support the assessment of a MTD based on descriptive summaries of safety and PK data. The sample size of up to 40 participants takes into account the differential tolerance in participants, some potentially tolerating 3000 mg daily, while others only tolerating lower dose levels. An effort will be made to enroll a number of subjects sufficient to ensure that at least 6 participants are treated at the study level MTD.

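### The automatic escalation pause counts similar related SAEs one dose level at a time, so up to four participants can share one before the 3000 mg step with no guaranteed pause or SMC review

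*Combined protocol and SAP*

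**What the plan says.** Section 3.2 describes the design: "This is an open-label, sequential period, within-participant dose escalation study". Participants start at 1500 mg/day and move up in three-week periods through 2000, 2500 and 3000 mg/day, then stay on their highest tolerated dose for a 24-week observation period.

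Three rules bear on serious events above 1500 mg/day:

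- **Related deaths (Section 3.7.1).** "The study will be put on hold immediately with the first fatal case reported in participants (at any dose level greater than 1500 mg/day"), if the death is considered related to study drug. This rule covers all levels above 1500 mg/day.
- **Similar related SAEs (Section 3.7.2, first bullet).** "If ≥ 3 participants at a given dose level experience similar and related serious adverse events (SAEs), dose escalation will be paused" until the SMC has assessed the data and made a recommendation. This rule counts within one level.
- **SMC discretion (Section 3.7.2, second bullet).** "Progression to the next higher dose level can also be stopped if the SMC recommends discontinuation of dose escalation". No event count is attached to it.

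For the affected participant, Section 3.7.3.1 lists a related SAE as a dose-limiting toxicity, after which "the Investigator should consider temporary dose reduction and/or study drug discontinuation for the individual participant after discussing with the Sponsor". On reporting, Section 9.2.1 states: "All SAEs must be reported within 24 hours of SAE awareness". On routine review, Section 3.2 says that the SMC "will review safety, tolerability, and available PK and PD data at regular intervals". Section 3.4 leaves the frequency of review to the SMC Charter, which is not among the documents.

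**The concern.** Section 3.7.2 speaks of cohorts, but the study has none: one group of participants climbs through the levels. Each level keeps its own running count, so similar events in that one group are divided over three counters, each with a threshold of three. A pattern of two cases at 2000 mg and one or two at 2500 mg leaves every counter below its threshold.

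The primary objective is tolerability and safety over the whole range from 2000 to 3000 mg/day. The highest multiple-dose regimen cited in the dose rationale (Section 1.5.2) is 1500 mg daily. A similar related SAE at two adjacent levels in this range is informative about the range, and the useful moment for a group-level look is before more participants step up. As written, that look depends on the SMC's regular schedule or on a decision to convene it.

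**Working it through.** **Is there a figure in the plan to reproduce?** No. The documents give no SAE rate and no operating characteristics for the pause rule. Section 10.2 derives the sample size from earlier experience in exploratory studies, without a formula.

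**Count from the wording.** At most 2 cases per level leave the rule untriggered.

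- Levels from which a participant can still step up (2000 and 2500 mg): 2 + 2 = 4 cases.
- All three levels: 2 + 2 + 2 = 6 cases. The last two occur at 3000 mg, so a pause after them protects only those who have not yet reached that dose.

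**Probability before the 3000 mg step.** Assumptions: N = 40 (Section 10.2 says up to 40); each participant has a total risk π of one similar related SAE above 1500 mg/day; π is split over 2000 : 2500 : 3000 mg. Three splits are used: 1:1:1, 1:2:3, and 3:3:27. The last is proportional to weeks on dose, with 3 + 24 = 27 weeks at 3000 mg.

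Let q₁ and q₂ be the shares of π at 2000 and 2500 mg. The chance of a cases at 2000 mg and b at 2500 mg is

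P(a, b) = N! / [a! b! (N − a − b)!] × q₁^a × q₂^b × (1 − q₁ − q₂)^(N − a − b).

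Three or more cases go untriggered when (a, b) is (2,1), (1,2) or (2,2). For π = 10% and the equal split, q₁ = q₂ = 0.0333:

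P(2,1) + P(1,2) + P(2,2) = 0.0855 + 0.0855 + 0.0565 = 0.227.

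The per-level rule fires with probability 1 − P(a ≤ 2 and b ≤ 2). A cumulative rule fires with probability 1 − P(a + b ≤ 2). For the equal split, N = 40, before 3000 mg:

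| Total risk π | Per-level rule fires | Cumulative rule fires | 3 or more cases, no pause |
|---|---|---|---|
| 2% | 0.5% | 1.6% | 1.1% |
| 4% | 3.2% | 9.0% | 5.8% |
| 5% | 5.7% | 14.8% | 9.1% |
| 10% | 27.6% | 50.4% | 22.7% |

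The last column is the difference between the two rules, up to rounding. It is both the benefit of a cumulative count and the number of extra reviews that it causes.

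**Sensitivity of the last column.**

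| Case | 1:1:1 | 1:2:3 | 3:3:27 |
|---|---|---|---|
| N = 40, π = 2% | 1.1% | 0.5% | 0.03% |
| N = 40, π = 4% | 5.8% | 2.7% | 0.2% |
| N = 40, π = 5% | 9.1% | 4.5% | 0.4% |
| N = 40, π = 10% | 22.7% | 15.0% | 2.5% |
| 40, 30, 20 start the three levels, π = 10% | 20.0% | 12.8% | 1.7% |
| N = 20, π = 10% | 9.0% | 4.4% | 0.4% |

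The fifth row is an illustration of the expectation in Section 10.2 that participants will differ, "some potentially tolerating 3000 mg daily, while others only tolerating lower dose levels". If all events fall at one level, the two counts agree and the gap is zero.

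**The case against.** The strongest reply is that the missing review would add little. The SMC is internal: Section 3.4 composes it of the Principal Investigator or designee and Sponsor staff, including the Medical Monitor. Every SAE is reported within 24 hours, and each related SAE during escalation above 1500 mg/day meets a dose-limiting toxicity criterion that is discussed with the Sponsor. The people who would sit on the SMC would largely know of the first, second and third case already. The SMC can stop escalation on all safety data taken together, the Sponsor can terminate the study at any time (Section 3.7.1), and Section 1.5.2 promises monitoring and assessment before each step. A per-level count also suits a study that looks for a maximum tolerated dose, because it ties toxicity to a dose. Finally, a cumulative trigger may already stand in the SMC Charter.

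Most of this stands, and it limits the weight of the point. A reader might infer that six participants could share a serious event with nobody noticing. The documents do not support that: reporting is prompt and the committee has the power to act. The pattern of six is also improbable, at most 1.3% at 10% total risk over all three levels.

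The reply does not remove the gap. The SMC and Sponsor powers are discretionary, the toxicity rule acts on the affected participant only, and reporting passes on information without obliging anyone to pause. The assessment promised in Section 1.5.2 is not assigned to the SMC. Followed exactly, Section 3.7.2 lets a pattern of 2 + 1 or 2 + 2 go by while others step up.

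**Conclusion.** The point holds as a small gap in a safety rule. The protocol text guarantees no pause and no timely SMC review when three or four participants share a non-fatal related SAE spread over 2000 and 2500 mg/day. Related deaths are already pooled over that range.

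The size rests wholly on assumed SAE rates. At N = 40 with an equal split, the chance of such a pattern before 3000 mg runs from about 1% (2% total risk) to 23% (10% total risk). The 10% case means about four of 40 participants sharing the same related SAE, which is a high assumption. The figures are also on the high side because 40 is a ceiling and because entry will be staggered: by the third case, some participants may already have reached 3000 mg and would gain nothing from a pause. If risk follows time on dose, so that most events fall at 3000 mg, the chance is 2.5% or less.

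A reader might also infer that the primary safety endpoint is compromised. It is not: collection and reporting of TEAEs and SAEs are unaffected. The right label is a cheap improvement of low priority.

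**What to change.** Keep the per-level rule and add one sentence to Section 3.7.2: escalation also pauses, until the SMC has reviewed the data, when 3 or more distinct participants have had similar related SAEs, counted cumulatively over all dose levels above 1500 mg/day and including SAEs in the observation period while any participant is still escalating. The per-level rule then matters mainly for 1500 mg. If the SMC Charter already contains this trigger, a cross-reference in Section 3.7.2 is enough.

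The change uses data already collected and needs no extra participants, visits or samples. Its cost is more SMC reviews. With N = 40, an equal split and observation-period SAEs left out, the chance of a pause before 3000 mg rises from 0.5% to 1.6% at 2% total risk, from 3% to 9% at 4%, and from 28% to 50% at 10%. Counting observation-period SAEs raises these figures. An upper bound is the chance of three or more cases over all levels, 1 − P(Binomial(40, π) ≤ 2): 4.6% at 2%, 21% at 4% and 78% at 10%. Each pause lasts only until the SMC has assessed the data.

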3.7.3. Early Discontinuation of Individual Participants

3.7.3.1. Individual Dose-limiting Toxicity Definition: Dose Escalation Period

Criteria for individual dose-limiting toxicity at doses beyond 1500 mg/day include, but are not limited to, the following:

- Any AE Grade ≥ 3 not clearly resulting from the underlying disease and deemed by the Investigator and/or Medical Monitor to be related to study drug.
- Worsening of an ongoing, treatment-related AE by ≥ 1 grade as per Investigator assessment
- Grade 3 nausea, vomiting, or diarrhea (deemed related to study drug) requiring hospitalization and/or intravenous fluids and parenteral tube feeding, total parenteral nutrition
- Study drug-related SAE

If any of these criteria is met, the Investigator should consider temporary dose reduction and/or study drug discontinuation for the individual participant after discussing with the Sponsor. If a subject discontinues early due to AEs, the subject will not be eligible for the open-label extension study.

3.7.3.2. Individual Early Discontinuation of Study Drug

Participants will be discontinued from study drug for any of the following reasons:

- Participant is lost to follow-up
- Discretion of the Investigator
- Participant is noncompliant
- Pregnancy
- Withdrawal of consent (participants are free to discontinue treatment or withdraw from the study at any time and for any reason. The Investigator must withdraw participants from the study who request to be withdrawn).

The participant should return to the study site for an EOS visit approximately 28 days after the last dose of study drug as indicated in Section 8.16. Subjects who discontinue study drug early will not be eligible for the open-label extension study.

4. SELECTION OF STUDY POPULATION

If a participant is found to meet inclusion/exclusion criteria at Screening but then has a clinically significant change in status prior to dosing (eg, hospitalized for sickle cell VOC, acute infection with drop in hemoglobin from participant's baseline), the participant should be withdrawn from screening and not administered study drug. The participant may be rescreened once at the Investigator's discretion and in consultation with the Sponsor. Participants who are rescreened will have all assessments repeated except for Hb genotyping.

4.1. Inclusion Criteria

Participants who meet all the following criteria will be eligible for enrollment in the study:

1. Male or female with SCD
2. Documentation of SCD genotype HbSS or HbSB⁰
3. Age 18 to < 60 years, inclusive
4. Hemoglobin ≥ 5.5 and ≤ 10.5 g/dL during Screening, and considered stable and close to Baseline by the Investigator
5. For participants taking HU, the dose in mg/kg must be stable for at least 90 days prior to signing the informed consent form (ICF) and with no anticipated need for dose adjustments during the study, in the opinion of the Investigator.
6. Participants, who if female and of child-bearing potential, agree to use highly effective methods of contraception or practicing abstinence from study start to 30 days after the last dose of study drug, and who if male, agree to use barrier methods of contraception or practice abstinence from study start to 30 days after the last dose of study drug
7. Participant has provided documented informed consent

4.2. Exclusion Criteria

Participants meeting any of the following exclusion criteria will not be eligible for study enrollment:

1. More than 10 VOCs within 12 months of screening that required a hospital, emergency room, or clinic visit
2. Female participant who is breast feeding or pregnant
3. Receiving regularly scheduled blood (RBC) transfusion therapy (also termed chronic, prophylactic, or preventive transfusion) or have received an RBC transfusion for any reason within 60 days of signing the ICF or at any time during the Screening Period
4. Hospitalized for sickle cell crisis or other vaso-occlusive event within 30 days prior to dosing (ie, a vaso-occlusive event cannot be within 30 days prior to dosing)
5. Screening laboratory test of alanine aminotransferase (ALT) $> 4 \times$ upper level of normal (ULN)
6. Clinically significant bacterial, fungal, parasitic, or viral infection which requires therapy, including acute bacterial infection requiring antibiotics

7. Known to be COVID-19 positive from within 3 weeks of screening through Day 1
8. Participants with active hepatitis A, B, or C or who are known to be human immunodeficiency virus (HIV) positive
9. Severe renal dysfunction (estimated glomerular filtration rate $< 30 \text{ mL/min/1.73 m}^2$ at the Screening visit; calculated by the local laboratory to assess safety) or is on chronic dialysis
10. History of malignancy within the past 2 years prior to treatment Day 1 requiring chemotherapy and/or radiation (with the exception of local therapy for non-melanoma skin malignancy)
11. History of unstable or deteriorating cardiac or pulmonary disease within 6 months prior to consent including but not limited to the following:
 - a. Unstable angina pectoris or myocardial infarction or elective coronary intervention
 - b. Congestive heart failure requiring hospitalization
 - c. Uncontrolled clinically significant arrhythmias
 - d. Pulmonary hypertension
12. Criteria related to ECG parameters:
 - a. PR interval $> 220 \text{ msec}$ in any participant
 - b. QRS interval $> 120 \text{ msec}$ or QT interval corrected using Fridericia's formula (QTcF) $> 480 \text{ msec}$ (both genders) in participants without bundle branch block
 - c. QRS interval $> 120 \text{ msec}$ in participants with newly (within 3 months) emerged bundle branch block
 - d. A participant with stable bundle branch block with or without stable cardiac disease may be enrolled; QRS interval $> 120 \text{ msec}$ and QTcF interval $> 480 \text{ msec}$ are acceptable in these participants.
13. Any condition affecting drug absorption, such as major surgery involving the stomach or small intestine (prior cholecystectomy is acceptable)
14. Participated in another clinical trial of an investigational agent or medical device within 30 days or 5 half-lives of date of informed consent, whichever is longer, or is currently participating in another trial of an investigational agent or medical device
15. Inadequate venous access as determined by the Investigator/site staff
16. Medical, psychological, or behavioral conditions, which, in the opinion of the Investigator, may preclude safe participation, confound study interpretation, interfere with compliance, or preclude informed consent
17. Received erythropoietin or other hematopoietic growth factor treatment within 28 days of signing ICF or is anticipated to require such agents during the study
18. Ongoing or recent (within 2 years) substance abuse
19. Known allergy to voxelotor
20. Use of herbal medications (eg, St. John's Wort), sensitive cytochrome P450 (CYP) 3A4 substrates with a narrow therapeutic index, strong CYP3A4 inhibitors, fluconazole, or moderate or strong CYP3A4 inducers.

